### 5.3.2. Caffeine, Alcohol, and Tobacco

- Participants will abstain from caffeine-containing products for 24 hours prior to the start of dosing until collection of the final PK sample of each study period.
- Participants will abstain from alcohol for 24 hours prior (except as stated above for red wine) to admission to the CRU and continue abstaining from alcohol until collection of the final PK sample of each study period. Participants may undergo an alcohol breath test or blood alcohol test at the discretion of the investigator.
- Participants will abstain from the use of tobacco- or nicotine-containing products for 24 hours prior to dosing and during confinement in the CRU.

### **5.3.3. Activity**

- Participants will abstain from strenuous exercise (eg, heavy lifting, weight training, calisthenics, aerobics) for at least 48 hours prior to each blood collection for clinical laboratory tests. Walking at a normal pace will be permitted;
- In order to standardize the conditions on PK sampling days, participants will be required to refrain from lying down (except when required for BP, respiratory rate, pulse rate, and ECG measurements), eating, and drinking beverages other than water during the first 4 hours after PF-07321332/ritonavir dosing;
- Participants will be confined to the procedure room for the first 4 hours after dosing on Day 1, except to use the bathroom. After this, participants may be ambulatory but should not engage in strenuous activities.

### **5.3.4. Contraception**

The investigator or his or her designee, in consultation with the participant, will confirm that the participant has selected an appropriate method of contraception for the individual participant and his or her partner(s) from the permitted list of contraception methods (see [Appendix 4 Section 10.4.4](#)) and will confirm that the participant has been instructed in its consistent and correct use. At time points indicated in the schedule of activities ([SoA](#)), the investigator or designee will inform the participant of the need to use highly effective contraception consistently and correctly and document the conversation and the participant's affirmation in the participant's chart (participants need to affirm their consistent and correct use of at least 1 of the selected methods of contraception) considering that their risk for pregnancy may have changed since the last visit. In addition, the investigator or designee will instruct the participant to call immediately if the selected contraception method is discontinued or if pregnancy is known or suspected in the participant or partner.

## **5.4. Screen Failures**

Screen failures are defined as participants who consent to participate in the clinical study but are not subsequently enrolled in the study. Screen failure data are collected and remain as source and are not reported on the CRF.

Individuals who do not meet the criteria for participation in this study (screen failure) may be rescreened.

## **6. STUDY INTERVENTION(S) AND CONCOMITANT THERAPY**

Study intervention is defined as any investigational intervention(s), marketed product(s), placebo, medical device(s), or study procedure(s) intended to be administered to a study participant according to the study protocol.

For the purposes of this protocol, study intervention refers to PF-07321332 and ritonavir.

## 6.1. Study Intervention(s) Administered

150 mg PF-07321332 tablets will be supplied by the sponsor to the CRU in bulk along with individual dosing containers for unit dosing.

Commercially available 100 mg ritonavir tablets will be supplied by the CRU.

### 6.1.1. Administration

Investigational products will be administered orally and according to the conditions described in the [SoA](#) section and Protocol Section [5.3.1 Meals and Dietary Restrictions](#).

For **fasted** period (Sequence 1, Period 1 and Sequence 2, Period 2):

- On Day -1, 12 hours prior to dosing of PF-07321332, participants will receive a 100 mg ritonavir tablet (as 1 × 100 mg) with approximately 240 mL ambient temperature water. On Day 1, following an overnight fast of at least 10 hours, the participants will receive 300 mg PF-07321332 (as 2 × 150 mg tablets) with 100 mg ritonavir (as 1 × 100 mg tablet) administered orally at approximately 08:00 hours (plus or minus 2 hours) without breakfast/standard meal on Day 1. 12 hours after dosing of PF-07321332, participants will receive a 100 mg ritonavir tablet (as 1 × 100 mg) with approximately 240 mL ambient temperature water.

For **fed** periods (Sequence 2, Period 1 and Sequence 1, Period 2):

- On Day -1, 12 hours prior to dosing of PF-07321332, participants will receive a 100 mg ritonavir tablet (as 1 × 100 mg) with approximately 240 mL ambient temperature water. On Day 1, following an overnight fast of at least 10 hours, participants will receive breakfast approximately 30 minutes prior to dosing which is to be completed within approximately 20 minutes as outlined in Section [5.3.1 \(Meals and Dietary Restrictions\)](#). The participants will then receive 300 mg PF-07321332 (as 2 × 150 mg tablets) with 100 mg ritonavir (as 1 × 100 mg tablet) administered orally at approximately 08:00 hours (plus or minus 2 hours). 12 hours after dosing of PF-07321332, participants will receive a 100 mg ritonavir tablet (as 1 × 100 mg) with approximately 240 mL ambient temperature water.

For **all** periods:

- PF-07321332 and ritonavir will be dosed simultaneously (within no more than 5 minutes of each other). Investigator site personnel will administer study intervention during each period with ambient temperature water to a total volume of approximately 240 mL. Participants will swallow all tablet formulations whole, and will not manipulate or chew the study intervention prior to swallowing.
- In order to standardize the conditions on PK sampling days, all participants will be required to refrain from lying down (except when required for BP, pulse rate, and ECG measurements), eating, and drinking beverages other than water during the first 4 hours after dosing.

## **6.2. Preparation, Handling, Storage, and Accountability**

1. The investigator or designee must confirm appropriate temperature conditions have been maintained during transit for all study interventions received and any discrepancies are reported and resolved before use of the study intervention.
2. Only participants enrolled in the study may receive study intervention and only authorized site staff may supply or administer study intervention. All study interventions must be stored in a secure, environmentally controlled, and monitored (manual or automated recording) area in accordance with the labeled storage conditions with access limited to the investigator and authorized site staff. At a minimum, daily minimum and maximum temperatures for all site storage locations must be documented and available upon request. Data for nonworking days must indicate the minimum and maximum temperatures since previously documented for all site storage locations upon return to business.
3. Any excursions from the study intervention label storage conditions should be reported to Pfizer upon discovery along with any actions taken. The site should actively pursue options for returning the study intervention to the storage conditions described in the labeling, as soon as possible. Once an excursion is identified, the study intervention must be quarantined and not used until Pfizer provides permission to use the study intervention. Specific details regarding the definition of an excursion and information the site should report for each excursion will be provided to the site in the CRU site procedures.
4. Any storage conditions stated in the SRSD will be superseded by the storage conditions stated on the label.
5. Study interventions should be stored in their original containers.
6. The investigator, institution, or the head of the medical institution (where applicable) is responsible for study intervention accountability, reconciliation, and record maintenance (ie, receipt, reconciliation, and final disposition records), such as the IPAL or sponsor-approved equivalent. All study interventions will be accounted for using a study intervention accountability form/record.
7. Further guidance and information for the final disposition of unused study interventions are provided in the CRU site procedures. All destruction must be adequately documented. If destruction is authorized to take place at the investigator site, the investigator must ensure that the materials are destroyed in compliance with applicable environmental regulations, institutional policy, and any special instructions provided by Pfizer.

Upon identification of a product complaint, notify the sponsor within 1 business day of discovery.

### **6.2.1. Preparation and Dispensing**

Within this protocol, preparation refers to the investigator site activities performed to make the study intervention ready for administration or dispensing to the participant by qualified staff. Dispensing is defined as the provision of study intervention, concomitant treatments, and accompanying information by qualified staff member(s) to a healthcare provider or participant in accordance with this protocol. Local health authority regulations or investigator site guidelines may use alternative terms for these activities.

PF-07321332 150 mg and ritonavir 100 mg tablets will be prepared at the CRU in the individual dosing containers by 2 operators, 1 of whom is an appropriately qualified and experienced member of the study staff (eg, physician, nurse, physician's assistant, nurse practitioner, pharmacy assistant/technician, or pharmacist). The tablets will be provided in unit dose containers and labeled in accordance with Pfizer regulations and the clinical site's labeling requirements.

### **6.3. Measures to Minimize Bias: Randomization and Blinding**

#### **6.3.1. Allocation to Study Intervention**

The investigator's knowledge of the treatment should not influence the decision to enroll a particular participant or affect the order in which participants are enrolled.

The investigator will assign participant numbers to the participants as they are screened for the study. Pfizer will provide a randomization schedule to the investigator and, in accordance with the randomization numbers, the participant will receive the study treatment regimen assigned to the corresponding randomization number.

### **6.4. Study Intervention Compliance**

When participants are dosed at the site, they will receive study intervention directly from the investigator or designee, under medical supervision. The date and time of each dose administered in the clinic will be recorded in the source documents and recorded in the CRF. The dose of study intervention and study participant identification will be confirmed at the time of dosing by a member of the study site staff other than the person administering the study intervention. Study site personnel will examine each participant's mouth to ensure that the study intervention was ingested.

### **6.5. Dose Modification**

No dose modification is anticipated.

### **6.6. Continued Access to Study Intervention After the End of the Study**

No intervention will be provided to study participants at the end of their study participation.

### **6.7. Treatment of Overdose**

For this study, any dose of PF-07321332 greater than 2250 mg or ritonavir greater than 200 mg within a 24-hour time period ( $\pm 2$  hours) will be considered an overdose.

There is no specific treatment for an overdose.

In the event of an overdose, the investigator should:

1. Contact the medical monitor within 24 hours.
2. Closely monitor the participant for any AEs/SAEs and laboratory abnormalities for at least 5 half-lives or 28 calendar days after the overdose of PF-07321332/ritonavir (whichever is longer).
3. Document the quantity of the excess dose as well as the duration of the overdose in the CRF.
4. Overdose is reportable to Pfizer Safety **only when associated with an SAE**.
5. Obtain a blood sample for PK analysis within 1 day from the date of the last dose of study intervention if requested by the medical monitor (determined on a case-by-case basis).

Decisions regarding dose interruptions or modifications will be made by the investigator in consultation with the medical monitor based on the clinical evaluation of the participant.

## 6.8. Concomitant Therapy

Participants will abstain from all concomitant treatments, except for the treatment of adverse events and hormonal contraceptives that meet the requirements of this study in participants who are WOCBP (see [Appendix 4](#)).

Use of prescription or nonprescription drugs and dietary and herbal supplements are prohibited within 7 days or 5 half-lives (whichever is longer) prior to the first dose of study intervention. Limited use of nonprescription medications that are not believed to affect participant safety or the overall results of the study may be permitted on a case-by-case basis following approval by the sponsor. Acetaminophen/paracetamol may be used at doses of  $\leq 1$  g/day.

As PF-07321332 and ritonavir are both primarily metabolized by CYP3A4, concomitant use of any medications or substances that are strong inducers of CYP3A4 are prohibited within 28 days prior to dosing of investigational product. Additionally, ritonavir and PF-07321332 are inhibitors of CYP3A4. Therefore, medications highly dependent on CYP3A4 for clearance and for which elevated plasma concentrations may be associated with serious and/or life-threatening events are not permitted during dosing of PF-07321332/ritonavir, through 4 days after the last dose of PF-07321332/ritonavir.

All concomitant treatments taken during the study must be recorded with indication, daily dose, and start and stop dates of administration. All participants will be questioned about concomitant treatment at each clinic visit.

Treatments taken within 28 days before the first dose of study intervention will be documented as a prior treatment. Treatments taken after the first dose of study intervention will be documented as concomitant treatments.

### **6.8.1. Rescue Medicine**

There is no rescue therapy to reverse the AEs observed with PF-07321332 or ritonavir; standard medical supportive care must be provided to manage the AEs.

## **7. DISCONTINUATION OF STUDY INTERVENTION AND PARTICIPANT DISCONTINUATION/WITHDRAWAL**

### **7.1. Discontinuation of Study Intervention**

It may be necessary for a participant to permanently discontinue study intervention. Reasons for permanent discontinuation of study intervention include the following.

- AE requiring discontinuation in investigator's view;
- Pregnancy;
- Positive COVID-19 test.

If study intervention is permanently discontinued, the participant will not remain in the study for further evaluation. See the [SoA](#) for data to be collected at the time of discontinuation of study intervention.

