- m. Single supine BP, RR and PR will be performed following at least a 5 minute rest in a supine position. BP, RR and PR assessments will be performed after collection of ECGs and prior to collection of blood draws if scheduled at the same time. Day 3 measurements are for Period 2 only. Temperature will be measured as per CRU standard practice.

PFIZER CONFIDENTIAL

Visit Identifier Abbreviations used in this table may be found in Appendix 8	Screening a	Periods 1-2 b												28-35 days (Follow-Up)	Early Termination/Discontinuation			
Days Relative to Day 1	Days -28 to -2	Day -1	Day 1										Day 2	Day 3	Day 28-35 w			
Hours After Dose			0	0.5	1	1.5	2	2.5	3	4	6	8	12	16	24	48		

n. Check exposure to positive participant, residence or travel in area of high incidence and COVID-19 related signs and symptoms.

o. The testing for COVID-19 pathogen by RT-PCR will be performed at each visit. For participants admitted for residence, a subsequent COVID-19 test will be performed after 4 days (ie, upon completion of 4 x 24 hours in house), or if they develop COVID-19 like symptoms.

p. Ritonavir will be administered orally -12 hours and 12 hours relative to PF-07321332/ritonavir dosing on Day 1.

q. PF-07321332/ritonavir will be administered orally after overnight fasting on Day 1 of each treatment period.

r. One (approximately 4 mL) blood sample for PK analysis of PF-07321332 will be taken at the designated time points post dose in each dosing period.

t. Participants will be discharged after collection of the 48-hour PK sample of period-2 dosing.

u. Period 1 only.

v. Collected at pre-dose for Period 1 only.

w. Contact may occur via telephone and must occur 28 to 35 days from administration of the final dose of study intervention.

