#### **7.1.1. Potential Cases of Acute Kidney Injury**

Abnormal values in SCr concurrent with presence or absence of increase in BUN that meet the criteria below, in the absence of other causes of kidney injury, are considered potential cases of acute kidney injury and should be considered important medical events.

An increase of  $\geq 0.3$  mg/dL (or  $\geq 26.5$   $\mu$ mol/L) in SCr level relative to the participant's own baseline measurement should trigger another assessment of SCr as soon as practically feasible, preferably within 48 hours from awareness.

If the second assessment (after the first observations of  $\geq 0.3$  mg/dL [or  $\geq 26.5$   $\mu$ mol/L] in SCr relative to the participant's own baseline measurement) is  $\geq 0.4$  mg/dL (or  $\geq 35.4$   $\mu$ mol/L), the participant should be discontinued from the study and adequate, immediate, supportive measures taken to correct apparent acute kidney injury.

Participants should return to the investigator site and be evaluated as soon as possible, preferably within 48 hours from awareness of the second assessment confirming abnormal SCr result. This evaluation should include laboratory tests, detailed history, and physical assessment. In addition to repeating SCr, laboratory tests should include serum BUN, serum creatine kinase, and serum electrolytes (including at a minimum potassium, sodium, phosphate/phosphorus, and calcium), in addition to urinary dipstick, urine microscopic examination, and urinary indices. All cases confirmed on repeat testing as meeting the

laboratory criteria for acute kidney injury, with no other cause(s) of laboratory abnormalities identified, should be considered potential cases of drug-induced kidney injury irrespective of availability of all the results of the investigations performed to determine etiology of the abnormal SCr. If  $\geq 2$  healthy participants are noted to have 2 consecutive SCr results of  $\geq 0.3$  mg/dL (or  $\geq 26.5$   $\mu$ mol/L), an assessment of whether the finding may be considered an adverse drug reaction should be undertaken.

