## **7.2. Participant Discontinuation/Withdrawal From the Study**

A participant may withdraw from the study at any time at his/her own request. Reasons for discontinuation from the study include the following:

- Refused further study procedures;
- Lost to follow-up;
- Death;
- Study terminated by sponsor;
- Investigator's decision;
- Pregnancy

At the time of discontinuing from the study, if possible, an early discontinuation visit should be conducted. See the [SoA](#) for assessments to be collected at the time of study discontinuation and follow-up and for any further evaluations that need to be completed.

The early discontinuation visit applies only to participants who are enrolled/randomized and then are prematurely withdrawn from the study. Participants should be questioned regarding their reason for withdrawal.

The participant will be permanently discontinued from the study intervention and the study at that time.

If a participant withdraws from the study, he/she may request destruction of any remaining samples taken and not tested, and the investigator must document any such requests in the site study records and notify the sponsor accordingly.

If the participant withdraws from the study and also withdraws consent (see Section 7.2.1) for disclosure of future information, no further evaluations should be performed and no additional data should be collected. The sponsor may retain and continue to use any data collected before such withdrawal of consent.

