### **7.2.1. Withdrawal of Consent**

Participants who request to discontinue receipt of study intervention will remain in the study and must continue to be followed for protocol-specified follow-up procedures. The only

exception to this is when a participant specifically withdraws consent for any further contact with him or her or persons previously authorized by the participant to provide this information. Participants should notify the investigator in writing of the decision to withdraw consent from future follow-up, whenever possible. The withdrawal of consent should be explained in detail in the medical records by the investigator, as to whether the withdrawal is only from further receipt of study intervention or also from study procedures and/or posttreatment study follow-up, and entered on the appropriate CRF page. In the event that vital status (whether the participant is alive or dead) is being measured, publicly available information should be used to determine vital status only as appropriately directed in accordance with local law.

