#### **8.3.1. Time Period and Frequency for Collecting AE and SAE Information**

The time period for actively eliciting and collecting AEs and SAEs (“active collection period”) for each participant begins from the time the participant provides informed consent, which is obtained before the participant’s participation in the study (ie, before undergoing any study-related procedure and/or receiving study intervention), through and including a minimum of 28 calendar days, except as indicated below, after the last administration of the study intervention.

Follow-up by the investigator continues throughout and after the active collection period and until the AE or SAE or its sequelae resolve or stabilize at a level acceptable to the investigator.

For participants who are screen failures, the active collection period ends when screen failure status is determined.

If the participant withdraws from the study and also withdraws consent for the collection of future information, the active collection period ends when consent is withdrawn.

If a participant permanently discontinues or temporarily discontinues study intervention because of an AE or SAE, the AE or SAE must be recorded on the CRF and the SAE reported using the CT SAE Report Form.

Investigators are not obligated to actively seek information on AEs or SAEs after the participant has concluded study participation. However, if the investigator learns of any SAE, including a death, at any time after a participant has completed the study, and he/she

considers the event to be reasonably related to the study intervention, the investigator must promptly report the SAE to Pfizer using the CT SAE Report Form.

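### Protocol 7.1, read literally, ends follow-up when study intervention is permanently stopped, which conflicts with the 28-day AE collection in 8.3.1 and the mandatory Day 28-35 contact

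*Protocol*

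**What the plan says.** Protocol section 7.1 gives reasons for permanently stopping study intervention: an AE that in the investigator's view requires it, pregnancy, and a positive COVID-19 test. The list is introduced as reasons that are included, so it is not exhaustive. The section then says: "If study intervention is permanently discontinued, the participant will not remain in the study for further evaluation". It points to the Schedule of Activities (SoA) only for data due at the time of discontinuation.

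Four other places bear on the same participants:

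- **Section 8.3.1** sets active AE and SAE collection for each participant from informed consent "through and including a minimum of 28 calendar days, except as indicated below, after the last administration of the study intervention". Two exceptions shorten it. One is screen failure. The other is a participant who "withdraws from the study and also withdraws consent for the collection of future information, the active collection period ends when consent is withdrawn".
- **SoA footnote w** says of the follow-up: "Contact may occur via telephone and must occur 28 to 35 days from administration of the final dose of study intervention". The synopsis and section 4.1 also plan this call and make no exception for early stoppers.
- **Section 7.2.1** says: "Participants who request to discontinue receipt of study intervention will remain in the study and must continue to be followed".
- **Section 7.2** sends those leaving the study to the SoA for "assessments to be collected at the time of study discontinuation and follow-up and for any further evaluations that need to be completed".

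**The concern.** A participant who stops dosing early is told to leave by one section and to be followed for four weeks by another, and the protocol states no order of precedence between them. The sentence in 7.1 has no exception for safety follow-up.

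A second sentence in 8.3.1 makes the literal reading easier to act on: "Investigators are not obligated to actively seek information on AEs or SAEs after the participant has concluded study participation". The protocol does not define when participation is concluded. A site that takes 7.1 at its word could treat participation as concluded at the early termination visit and make no further contact.

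What could be lost is any new adverse event that starts after that visit. The first reason listed in 7.1 is an AE, so the participants concerned include those whose later safety information matters most. Safety and tolerability, including TEAEs, is a secondary objective. SAP section 3.5.1 flags as treatment-emergent any event starting from first dosing until the end of the study, so an event in this window would count if it were collected.

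**Working it through.** The plan gives no figure on this point and none is needed. The check is a comparison of the texts.

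**1. Does 8.3.1 exempt early stoppers?** No. The only events that end collection early are screen failure, and withdrawal from the study together with withdrawal of consent. Section 8.3.1 does mention permanent discontinuation because of an AE, but only to require that the event be recorded and, if serious, reported. It does not shorten the window.

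**2. Does footnote w exempt them?** No. It counts from the final dose of study intervention, which an early stopper also has, and makes the contact obligatory.

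**3. Does the SoA reference in 7.1 restore follow-up?** No. It covers data collected when the intervention is stopped, not afterwards.

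**4. Does 7.2.1 contradict 7.1?** In part. Section 7.2.1 concerns participants who ask to stop dosing. The reasons listed in 7.1 are ones where stopping may become necessary. Because that list is open and the closing sentence of 7.1 applies to every permanent discontinuation, the two conflict for participant-requested stops. They do not conflict for the three listed reasons.

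**5. What does the rest of the protocol suggest was intended?** Continued safety follow-up. Section 7.1.1, a subsection of 7.1, says that after a confirmed creatinine rise "the participant should be discontinued from the study and adequate, immediate, supportive measures taken to correct apparent acute kidney injury", and then recalls that participant to the site for laboratory tests, history and examination. Section 7.2 refers those who leave the study to the SoA for follow-up, and bars further evaluation only where consent is withdrawn as well.

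**6. What stays protected under the literal reading?** The AE that led to the stop is followed until it resolves, stabilizes or is otherwise explained, or the participant is lost to follow-up (8.3.3). Suspected kidney injury is re-evaluated (7.1.1). A pregnancy is followed to its outcome (8.3.5.1). A related SAE that the investigator learns of later must be reported (8.3.1). The exposed part is therefore new events, not already known at the early termination visit, that nobody asks about.

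**7. Is the primary analysis touched?** No. A participant who has permanently stopped receives no further dosing under either reading, and the Day 28-35 contact supplies no PK data.

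**The case against.** The strongest reply is that the sections can be reconciled. Collection under 8.3.1 does not depend on remaining in the study: leaving ends it only if consent is also withdrawn, and 7.2 is built the same way. On that view, further evaluation in 7.1 means remaining treatment periods and PK sampling, and 8.3.1 governs AE collection throughout. Section 7.1.1 uses similar language and still recalls the participant. The undefined phrase about concluded participation is followed by a sentence on participants who have completed the study, and section 4.4 defines completion to include the last scheduled SoA procedure. A site would have to let one general sentence override 8.3.1, footnote w, and the call planned in the synopsis and section 4.1.

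Much of this stands. It is the better account of the intent, and it keeps the point small. It does not remove the point, because 7.1 is the section a site consults when stopping a participant, and that section neither limits its sentence to dosing and PK nor refers to 8.3.1. Section 4.4 defines completion, which does not settle when someone who stops early has concluded participation.

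A reader might go further and infer that the protocol actually ends AE collection for everyone who stops early. The documents do not support that, given sections 7.1.1, 7.2 and the two-part consent exception in 8.3.1.

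**Conclusion.** The 7.1 sentence is wrong as written: read literally, it conflicts with 8.3.1 and with SoA footnote w, and for participant-requested stops with 7.2.1. Severity is minor. The consequence is possible loss of new adverse events after the early termination visit, in whichever of about 12 participants stop early. It affects secondary safety ascertainment only.

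This rests on one assumption, that a site might apply 7.1 literally. The protocol neither rules that out nor intends it.

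A reader might want to express the gap as days of lost observation, or as time within the drug's elimination period. The documents do not support such a figure. They do not fix when an early termination visit takes place or which dose would be a stopped participant's last, and the visible text gives no expected discontinuation rate. No number of affected participants is claimed.

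**What to change.** Replace the sentence in 7.1 with:

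*If study intervention is permanently discontinued, the participant will receive no further dosing, will complete the Early Termination/Discontinuation assessments in the SoA, and will remain in safety follow-up through the Day 28-35 contact per Section 8.3.1, unless consent for further contact is withdrawn.*

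Optionally, add a cross-reference in 7.2 saying that AE and SAE collection after study discontinuation follows 8.3.1 where the participant can be contacted and has not withdrawn consent.

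The new 7.1 sentence agrees with 7.2.1. It also makes clear that an early stopper has not concluded participation before the Day 28-35 contact, so the related sentence in 8.3.1 can stay as it is.

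The cost is one replaced sentence and, if wanted, one cross-reference. No procedure is added: the only operational consequence is one contact per affected participant, which may be by telephone and which the SoA already requires.
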